9.3 Sensitivity Analysis

The sensitivity analysis for primary efficacy endpoint will be performed by excluding all subjects from site CZ03 due to GCP compliance issues at this site. These subjects will be excluded from

both ITT and PP populations as another analysis scenario (ITT excluding subjects from site CZ03, and PP excluding subjects from site CZ03) for sensitivity analysis.

The summary results will be presented as Table 14.2.25~Table 14.2.26 and Table 14.2.27~Table 14.2.28 for ITT and PP populations.

10. EXTENT OF EXPOSURE AND DRUG COMPLIANCE

The study treatment LMIS 25 mg will be administered on Day 0 (Visit 2) and Day 84 (Visit 13; week 12). The study treatment date, time will be listed by subject in Listing 16.2.5.1. The proportion of subjects received first and second administration will be provided as Table 14.1.1.

11. SAFETY ANALYSIS

11.1 Adverse Events

All AEs will be coded by system organ class and preferred term for analysis. Treatment-emergent adverse event (TEAE) is defined as AEs occur after the first administration of study drug, or AEs occur before the first administration of study drug and worsen in severity after first dose. Unless otherwise specified, all adverse event summaries will include the TEAEs only. For purposes of the summary tables, AEs will be classified as either related or not related to study drug. The drug-related AEs are assessed as 'Definite', or 'Possible' related to study treatment. If the relationship is missing, the AE will also be assessed as drug-related AE. This summary will present the number and percentage of subjects, as well as number of events. For subject with the same AE but multiple different severity/relationship (which resolution date=onset date or resolution date=onset date+1, except they have different AE No), the multiple event will be combined as one AE with the maximum severity/ relationship category for analysis.

A general summary includes number of events, number and percentage of subjects reporting adverse events of all TEAEs will be provided in Table 14.3.1.1.1 according to the following categories:

- Subject with any TEAE
- Subject with any drug-related TEAE

Also, a general summary of all TEAEs will be provided in Table 14.3.1.1.2 according to the following categories:

- TEAEs by severity
- TEAEs by relationship
- Serious TEAEs

- Drug-related TEAEs by severity

Other summary tables for adverse events will be summarized by MedDRA system organ class and preferred term include:

Table 14.3.1.2: Treatment-Emergent Adverse Events - MedDRA

Table 14.3.1.3: Treatment-Emergent Adverse Events by Severity - MedDRA

Table 14.3.1.4: Treatment-Emergent Adverse Events by Relationship to Study Drug - MedDRA

Table 14.3.1.5: Treatment-Emergent Adverse Events for Grade ≥ 3 – MedDRA

Table 14.3.1.6: Drug-Related Treatment-Emergent Adverse Events by Severity – MedDRA

Table 14.3.1.9: Treatment-Emergent Adverse Events - MedDRA (Preferred Term over XX %)

The listing of all AEs will be provided in Listing 16.2.7.1. In addition, TEAEs leading to study discontinuation will be provided in Listing 16.2.7.2.

11.2 Serious Adverse Event

The summary of SAEs will be presented by MedDRA system organ class and preferred term, and this summary will present the number and percentage of subjects, as well as number of events:

Table 14.3.1.7: Treatment-Emergent Serious Adverse Events - MedDRA

Table 14.3.1.8: Treatment-Emergent Serious Adverse Events by Relationship to Study Drug - MedDRA

A listing of all serious adverse events will be provided in Listing 16.2.7.3.

11.3 Laboratory Evaluation

Clinical laboratory tests included hematology, biochemistry and urinalysis.

Hematology tests include complete blood count (CBC), Hb, Hct, RBC count, WBC count, WBC differential (neutrophils, eosinophils, basophils, lymphocytes, and monocytes), platelet count, and HbA1c.

Biochemistry tests include ALT, AST, ALP, total bilirubin, BUN, Serum Cr, electrolytes (K, Na, Mg, Ca and P), blood glucose, and lipid profile (LDL, HDL, triglycerides)

Urinalysis tests include pH, specific gravity, leukocyte, erythrocyte, urine glucose, nitrate, and protein..

By-subject-visit listings of measured values for clinical laboratory test data (hematology, biochemistry and urinalysis) will be prepared in Listing 16.2.8.1 ~ Listing 16.2.8.3. Observations outside the normal range will be flagged. The abnormal values will be flagged with 'L' (low) for

Statistical Analysis Plan

values below the lower limit of the laboratory's normal range, 'H' (high) for values above the upper limit of the laboratory's normal range or 'A' for values out of the laboratory's normal range. The abnormal values for clinical laboratory test data (hematology, biochemistry and urinalysis) will be prepared in [Table 14.3.4](#). The record with observed value of clinical laboratory data below or above the detection limit will be imputed with the detection limit for analysis.

The baseline is defined as the last observation prior to first dose unless otherwise specified. The summary results of laboratory data (hematology, biochemistry and urinalysis) at baseline, EOS/ET Visit and change from baseline to the EOS/ET Visit will be summarized by descriptive statistics and paired t-test or Wilcoxon signed-rank test with significance level at 0.05. Results will be presented in [Table 14.3.5.1~Table 14.3.5.3](#). The transition matrix of change in laboratory data (normal, abnormal NCS and abnormal CS status) between baseline and the EOS/ET Visit will be summarized as [Table 14.3.5.4~Table 14.3.5.6](#).

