7.3.3. Hematological / biochemistry examinations

The safety profile of LMIS 25 mg will be assessed using lab test including hematological and biological examinations by collecting blood samples from all subjects.

Hematological tests will include complete blood count (CBC): hemoglobin (Hb), hematocrit (Hct), red blood cells (RBC), white blood cells (WBC), WBC differential (neutrophils, eosinophils, basophils, lymphocytes, and monocytes), platelet counts, and HbA1c. Biochemistry tests will include ALT, AST, ALP, total bilirubin, BUN, Serum Cr, electrolytes (K, Na, Mg, Ca and P), blood glucose and lipid profile (LDL, HDL, triglycerides).

Laboratory tests, except for the HbA1c, will be performed during the screening visit and on Day 0 (prior to dosing), Day 14 ± 1 day (week 2), Day 28 ± 1 day (week 4), Day 84 ± 1 (prior to dosing, week 12), and Day 168 ± 5 days (week 24, EOS/ET).

The HbA1c will be performed at the screening visit and at the final visit (Day 168, week 24, or End of Study Visit/Early termination).

Blood samples for laboratory tests will be collected and will be sent to the Central Laboratory for analyses.

Protocol No.: FP01C-17-001

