7.3.4. Urinalysis

Urinalysis will be collected from all subjects to assess the safety profile of LMIS 25 mg. The urinalyses will include urine pH, specific gravity, leukocyte, erythrocyte, urine glucose, nitrate, and protein.

The urinalysis will be performed at screening, Day 0 (prior to dosing), Day 14 ± 1 day (week 2), Day 28 ± 1 day (week 4), Day 84 ± 1 (prior to dosing, week 12), and Day 168 ± 5 days (week 24, EOS/ET).

Urine samples will be collected and sent to the Central Laboratory for analyses.

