10.5. Safety Analysis

The safety analysis of LMIS 25 mg will be based on the following safety assessments:

- Adverse event (AE)/serious adverse event (SAE) reporting

The analysis of AEs will be tabulated by system organ class (SOC) and preferred terms according to the current MedDRA dictionary. Preferred terms will be used and presented as standardized tabulations by frequency and incidence rates. AE incidence rates will be analyzed by severity and relationship to study drug. Any AE leading to death, discontinuation from the study, or change of dose will be listed as per regulations. If any SAE occurs, a summary of the SAEs will be described and listed.

- Assessment of injection site reaction

The local injection site reaction will be summarized descriptively.

- Change in bone pain measurement (by Visual Analogue Scale [VAS] scale)
- Change in urinary signs and symptoms and the total score between baseline (Day 0) and Day 168 \pm 5 (days, week 24) (by the International Prostate Symptom Score, I-PSS sheet)

The summary results of bone pain measurement (by VAS scale) at baseline (Day 0), end of study visit (EOS/ET, Day 168 \pm 5 days, week 24), and the change from baseline will be summarized descriptively. The change from baseline to EOS visit will be tested by paired t-test or Wilcoxon signed-rank test at a significance level of 0.05. The urinary signs and symptoms (by the International Prostate Symptom Score, I-PSS, sheet) at baseline (Day 0) and EOS/ET visit (Day 168 \pm 5 days, week 24) will be summarized descriptively

- Change in vital signs (BP, HR, RR, weight)
- Change in physical examinations with clinical significance compared to baseline by principal investigator's judgment

The summary results of change in physical examinations with clinical significance vital signs (BP, HR, RR) and weight at baseline (Day 0), EOS/ET Visit (Day 168 \pm 5 days, week 24), and the change from baseline will be summarized descriptively. Also the change from baseline (Day 0) to the EOS/ET Visit (Day 168 \pm 5 days, week 24), will be tested by paired t-test or Wilcoxon signed-rank test at a significance level of 0.05. The transition matrix of physical examination and change in vital signs will be summarized.

- Change in lab data, including liver function (AST, ALT, ALP), renal function (BUN, S_{Cr}), complete blood count with platelets, clinical chemistries (K, Na, Mg, Ca and P), urinalysis, serum glucose, lipid profile (LDL, HDL, triglycerides), and HbA1c level

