The summary results of laboratory data at baseline (Day 0) and the EOS Visit (Day 168 \pm 5 days, week 24) and change from baseline (Day 0) to the EOS/ET Visit (Day 168 \pm 5 days, week 24) will be summarized by descriptive statistics and paired t-test or Wilcoxon signed-rank test and will be used at a significance level of 0.05. The transition matrix of change in laboratory data between baseline (Day 0) and the EOS/ET Visit (Day 168 \pm 5 days, week 24) will be summarized.

- Clinically significant changes in 12-lead resting electrocardiogram (ECG) per the investigator's judgment

The summary results of 12-lead resting ECG at baseline (Day 0) and the EOS/ET Visit (Day 168 ± 5 days, week 24) will be summarized descriptively. The transition matrix for ECGs will be summarized.

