11.4 Vital Signs and Physical Examination

Vital Signs

Individual subject vital signs (height, weight, body pressure, heart rate, respiration rate and body temperature) will be listed in [Listing 16.4.1](#).

The baseline is defined as the last observation prior to first dose unless otherwise specified. The summary results of vital signs (body pressure, heart rate, respiration rate and body temperature) and weight at baseline, EOS/ET Visit, and the change from baseline will be summarized descriptively. Also the change from baseline to the EOS/ET Visit will be tested by paired t-test or Wilcoxon signed-rank test at a significance level of 0.05 in [Table 14.3.6](#).

Physical Examination

Physical examination data (included: General appearance, Skin, Eyes, Ear/ Nose/ Throat (ENT), Head, Neck, Heart, Chest, Lungs, Abdomen, Extremities, Lymph nodes, Musculoskeletal and Neurological) will be listed in [Listing 16.4.2](#), and will be summarized descriptively as count and percentage in [Table 14.3.7.1](#). The transition matrix of physical examination (normal, abnormal NCS and abnormal CS status) will be summarized in [Table 14.3.7.2](#).

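### Laboratory and vital-sign change is summarised only from baseline to EOS/ET, so interim visits enter no aggregate change or shift table, and the vital-sign transition matrix named in protocol 10.5 is missing from the SAP

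*SAP*

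**What the plan says.** **Laboratory analysis.** SAP 11.3 describes and tests, in Tables 14.3.5.1 to 14.3.5.3, "The summary results of laboratory data (hematology, biochemistry and urinalysis) at baseline, EOS/ET Visit and change from baseline to the EOS/ET Visit". For Tables 14.3.5.4 to 14.3.5.6 it specifies "The transition matrix of change in laboratory data (normal, abnormal NCS and abnormal CS status) between baseline and the EOS/ET Visit". Protocol 10.5 uses the same two ends: "The transition matrix of change in laboratory data between baseline (Day 0) and the EOS/ET Visit". The restriction was therefore planned in the protocol and carried over.

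**Laboratory schedule.** Protocol 7.3.3 states: "Laboratory tests, except for the HbA1c, will be performed during the screening visit and on Day 0". It then lists "Day 14 ± 1 day (week 2), Day 28 ± 1 day (week 4), Day 84 ± 1 (prior to dosing, week 12") and the Day 168 or early-termination visit. Protocol 7.3.4 gives urinalysis the same days: "The urinalysis will be performed at screening, Day 0 (prior to dosing), Day 14 ± 1 day (week 2") and onward. HbA1c is taken only at screening and at the final visit.

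**Vital signs.** Protocol 7.3.1 has them measured at every visit, and weight at screening, Day 84 and Day 168. SAP 11.4 summarises baseline, EOS/ET and change in Table 14.3.6, and adds: "Also the change from baseline to the EOS/ET Visit will be tested by paired t-test or Wilcoxon signed-rank test". Protocol 10.5 also says: "The transition matrix of physical examination and change in vital signs will be summarized". In SAP 11.4 the only transition matrix (Table 14.3.7.2) is for physical examination. SAP section 1 says that the SAP prevails where the two documents differ.

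**The concern.** Safety over up to 24 weeks is half of the primary objective (protocol 2.1.1, SAP 2). A comparison of baseline with the last visit answers only whether subjects leave the study changed. It does not show, in aggregate, what happened between those points. A laboratory value that is normal at baseline, abnormal on Day 14 or 28 and normal again on Day 168 is counted as normal to normal.

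Protocol 5.5 itself names effects that need not be visible only at the end: a testosterone flare in the first week, reduced glucose tolerance and anemia. Protocol 1.3 reports hypertension as the second most common treatment-emergent event in the LMIS 50 mg study (14.6% of 137 subjects). Here blood pressure is taken at every visit, yet only the last reading is compared with baseline.

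At stake is how complete the safety tables are. The primary efficacy analysis and the sample size do not depend on it.

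**Working it through.** The plan states no figure to reproduce on this point. The check sets the assessment schedule against the tables and counts what falls outside them.

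**Laboratory data (protocol 7.3.3 and 7.3.4).**
- Scheduled draws after the first dose: Days 14, 28, 84 and 168, so 4.
- Draws used in the change and shift tables: Day 168 (EOS/ET), so 1.
- Unused: 4 − 1 = 3 of 4. HbA1c has only one post-dose measurement, so nothing is lost for it.

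**Vital signs, subjects outside the first 30 (protocol Tables 1a and 1b).**
- Visits 3 to 22 are 20 visits. Visits 10 and 19 are for the first 30 subjects only, which leaves 20 − 2 = 18.
- Visits used in Table 14.3.6: Visit 22, so 1. Unused: 17 of 18.

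**Vital signs, first 30 subjects.** Visits 3 to 23 are 21 visits; one is used, so 20 of 21 are unused.

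**Weight.** It is measured after dosing only on Days 84 and 168, so 1 of 2 is unused. The counts above do not apply to it.

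**When the laboratory draws could show an early effect.** Days 14 and 28 follow the first injection. Day 84 is taken before the second injection, and the only later scheduled draw is Day 168. So scheduled laboratory data can show early post-dose change after the first injection only. Vital signs are also taken on Days 85 to 87, 98 and 112, so they can show it after both.

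**Where an interim abnormality appears.**

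| Output | Laboratory | Vital signs |
|---|---|---|
| By-subject listing | Yes, with out-of-range flags (Listings 16.2.8.1 to 16.2.8.3) | Yes (Listing 16.4.1) |
| Abnormal-value table | Table 14.3.4; no limit to EOS/ET is stated, and no comparison with baseline is described | None |
| Adverse-event tables | If action is needed or the investigator judges the value clinically significant (protocol 9.1) | If detected and reported as an event (protocol 9.1) |
| Change table by visit | None | None, except heart rate from the ECG |
| Shift or transition table | Baseline to EOS/ET only | None at all |

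**How the SAP treats ECG.** SAP 11.5 summarises ECG change from baseline at each visit and time point. It also classifies the maximum or minimum post-dose value. Both methods proposed below are therefore already in the SAP for another safety domain.

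**Direction of the effect.** For a subject with an EOS/ET value, the worst of all scheduled post-baseline values, EOS/ET included, cannot be less abnormal than the EOS/ET value itself. The number of subjects with a shift to abnormal can therefore only stay the same or rise. The documents hold no data from which to derive by how much.

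**The case against.** The strongest reply is that this is a matter of tabulation and nothing is hidden. Every interim laboratory value is listed and flagged, Table 14.3.4 presents abnormal values, and clinically important ones become adverse events that are tabulated by severity and relationship. The 14.6% for hypertension in the LMIS 50 mg study shows that adverse-event reporting does pick up blood-pressure findings. Protocol and SAP also agree on the laboratory comparison, and the endpoint of change in laboratory data prescribes no by-visit or worst-value method. All of this stands. It limits the point to aggregate summaries, but does not remove it: listings give no rates, and neither Table 14.3.4 nor the adverse-event tables are described as comparing with baseline.

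Four stronger readings are tempting and are not supported:

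- **Interim toxicity goes unreported.** The outputs just named show it.
- **Laboratory peaks after each injection are lost.** No laboratory draw is scheduled between the pre-dose Day 84 sample and Day 168, so no table of scheduled values could show a peak after the second injection.
- **Vital-sign shifts are analysed to EOS/ET only.** The SAP has no vital-sign shift table at all, although the protocol names a matrix.
- **No vital sign is summarised by visit.** Heart rate is covered in the separate ECG report, by time point and with outlier criteria that include a change from baseline.

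Two passages could be read more generously. SAP 11.4 names no visit where it says that vital-sign change will be described, but the rest of that sentence and the test both refer to EOS/ET. Protocol synopsis X.5(10) is also silent on visits, but the more specific SAP prevails.

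There is also a fair objection to worst-value tables that pool unscheduled results: for-cause retests would inflate the counts. The fix allows for this.

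**Conclusion.** The point holds as a gap in aggregate change and shift summaries. Three of four post-dose laboratory draws, and 17 of 18 post-dose vital-sign visits (20 of 21 in the first 30 subjects), enter no such table. The vital-sign transition matrix named in protocol 10.5 has no counterpart in SAP 11.4. For laboratory data the SAP follows the protocol, so that part is an improvement to a consistent plan. The missing vital-sign matrix is a discrepancy between the two documents.

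The severity is low: a worthwhile and cheap addition that serves the safety half of the primary objective and changes no efficacy conclusion. The conclusion assumes that Table 14.3.4 is what its one-sentence description suggests, a presentation of abnormal values without comparison with baseline. If its layout already gives shifts by visit, the laboratory part shrinks accordingly. How many subjects would move from normal-to-normal to a shift cannot be derived from the documents.

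**What to change.** Keep all EOS/ET tables and tests as they are. Then:

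1. **SAP 11.3:** add descriptive change from baseline at Days 14, 28, 84 and EOS/ET, and a shift from baseline to the worst scheduled post-baseline category, using the existing normal, abnormal NCS and abnormal CS classes. Count the EOS/ET visit among the scheduled values. HbA1c needs no addition.
2. **SAP 11.4:** add by-visit change from baseline, and summaries from baseline to the maximum and minimum post-baseline value. For weight this adds Day 84 only.
3. **SAP 11.4:** restore the vital-sign transition matrix named in protocol 10.5, or state and justify its removal. The documents give no categories for it, so the SAP must define them before the data are summarised.
4. **Unscheduled values:** show worst-value counts that include them separately from those based on scheduled visits. The SAP at present only lists unscheduled assessments (Listing 16.4.9).

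The cost is a few more tables from data already collected. There is no new sampling and no effect on sample size. Shift-to-abnormal counts will stay the same or rise, and the text accompanying the tables should explain that a worst-value count and an end-of-study count answer different questions.

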11.4 Vital Signs and Physical Examination

Vital Signs

Individual subject vital signs (height, weight, body pressure, heart rate, respiration rate and body temperature) will be listed in [Listing 16.4.1](#).

The baseline is defined as the last observation prior to first dose unless otherwise specified. The summary results of vital signs (body pressure, heart rate, respiration rate and body temperature) and weight at baseline, EOS/ET Visit, and the change from baseline will be summarized descriptively. Also the change from baseline to the EOS/ET Visit will be tested by paired t-test or Wilcoxon signed-rank test at a significance level of 0.05 in [Table 14.3.6](#).

Physical Examination

Physical examination data (included: General appearance, Skin, Eyes, Ear/ Nose/ Throat (ENT), Head, Neck, Heart, Chest, Lungs, Abdomen, Extremities, Lymph nodes, Musculoskeletal and Neurological) will be listed in [Listing 16.4.2](#), and will be summarized descriptively as count and percentage in [Table 14.3.7.1](#). The transition matrix of physical examination (normal, abnormal NCS and abnormal CS status) will be summarized in [Table 14.3.7.2](#).

11.5 Other Variables Related to Safety

Concomitant Medication and Non-Drug Therapy

Individual subject concomitant medication and non-drug therapy will be listed in [Listing 16.2.5.2](#).

12-Lead ECG

Individual subject 12-Lead ECG data (heart rate, PR interval, RR interval, QRS duration, QT, QTc and overall interpretation) will be listed in Listing 16.4.3.

The baseline is defined as the last observation prior to first dose unless otherwise specified. The summary results of 12-lead resting ECG at baseline, EOS/ET Visit will be summarized descriptively in Table 14.3.8.1. The transition matrix for ECGs overall interpretation (normal, abnormal NCS and abnormal CS status) will be summarized in Table 14.3.8.2.

Additional 12-Lead ECG and PK Analyses for ECG Report

A separate ECG report will be provided with the results of the analyses in this section.

The following corrected QT interval for each visit and time point will be derived and considered the primary ECG assessment for the analysis in the ECG report.

QTcF: The QT interval in units of milliseconds (msec) corrected by the Fridericia formula will be calculated as follows:

$$QTcF = \frac{QT}{\sqrt[3]{RR}}, \text{ where RR interval will be expressed in units of seconds.}$$

Descriptive statistics (number of subjects, mean, SD, 2-sided CI [90% for the QTcF interval or 95% for other parameters], median, 25th percentile, 75th percentile, minimum, and maximum) will be provided for baseline and each visit and time point post dose for results and change from baseline, denoted as ΔECG (i.e. $\Delta QTcF$, ΔHR , ΔPR , ΔQRS), for the ECG population. Missing data will not be imputed. Unscheduled data will not be summarized or included in analyses. The means and 90% (in the case of $\Delta QTcF$) or 95% CIs for the ΔHR , ΔPR , and ΔQRS values, will be displayed graphically by scheduled day and time point.

An analysis will be provided for the PK/ECG population based on a linear mixed effects model. The mixed-effects model will contain $\Delta QTcF$ as the dependent variable and include the corresponding leuprolide or testosterone serum concentrations in separate models with a random intercept and slope, day/time point as a categorical variable, and baseline QTcF (adjusted for the overall mean of subjects' baseline data included in the model) as the independent variables. The mixed effects model will be used to estimate, for all subjects in the PK/ECG analysis population, the predicted population mean $\Delta QTcF$ and its corresponding 2-sided 90% CI at mean C_{max} of the serum concentrations. Serum concentration values reported as below the limit of quantitation (BLQ) will be assigned a value of zero in this analysis. This analysis will be repeated for ΔHR , ΔPR , and ΔQRS , but 95% CIs will be presented rather than 90%.

Statistical Analysis Plan

The adequacy of the linear assumption between Δ ECG interval and serum concentrations will be determined by adding a quadratic term to the mixed-effects model. If the quadratic term is different than zero, having a p-value <0.05 , and an Akaike's information criteria (AIC) that is smaller in comparison to the linear model's AIC, then a quadratic term may be added. In addition, a transformation of the concentrations [e.g. $\log(\text{Concentration}/\text{LLOQ})$, where LLOQ is the lower limit of quantitation of the assay and all values below the LLOQ are replaced with the LLOQ] may also be assessed. The best model fit will be determined by the lowest AIC, unless the model results are not clinically or physiologically sensible.

If convergence cannot be reached, adjustment to the model as follows will be considered: the random slope may be removed, an alternative covariance structure attempted, or as a last resort, the removal of the time effect may be considered.

The relevant SAS code statements are:

```
PROC MIXED DATA = DATA METHOD=REML;
  CLASS SUBJID ATPTN;
  MODEL CHG = CONC ATPTN BASEADJ /NOINT SOLUTION OUTP=PRED;
  RANDOM INTERCEPT CONC /TYPE=UN SUBJECT=SUBJID;
  ESTIMATE ' $\Delta$ ECG at Cmax' CONC xx.x / CL ALPHA=0.1;
RUN;
```

In the above statements:

- CHG represents the Δ QTcF value (or corresponding secondary parameter);
- CONC represents measured serum concentrations of leuprolide or testosterone;
- ATPTN represents the day/time point;
- BASEADJ represents the numeric baseline minus the overall mean of all baseline values for the ECG parameter;
- TYPE=UN means that an unstructured covariance matrix will be used for the correlated random effects (INTERCEPT and CONC);
- xx.x in the ESTIMATE statement represents the estimated arithmetic mean C_{max} for leuprolide or testosterone.

Categorical Analyses for ECG Report

Categorical analyses of HR, PR, QRS, and QTcF will be performed to determine the number and percentage of subjects, who meet each of the following criteria at each day/time point and at the maximum/minimum QTcF (HR, PR or QRS) value postdose:

- Result QTcF ≤ 450 , >450 and ≤ 480 , >480 and ≤ 500 , and >500 msec;

Statistical Analysis Plan

- Change from baseline $\Delta\text{QTcF} \leq 30$, >30 and ≤ 60 , and >60 msec;
- PR Outliers (PR >200 msec and a 25% or greater increase from baseline);
- QRS Outliers (QRS >100 msec and a 25% or greater increase from baseline);
- HR Outliers (HR <50 beats/min and a 25% or greater decrease from baseline);
- HR Outliers (HR >100 beats/min and a 25% or greater increase from baseline).

Morphological ECG Diagnostic Statement Analyses for ECG Report

Abnormal morphological diagnostic statements will be tallied and tabulated for each day/time point and overall. The incidence rate of abnormal diagnostic statements will be tabulated for both baseline and post dose assessments, and also tabulated with abnormal diagnostic statements categorized as treatment emergent diagnostic statements (i.e., abnormal diagnostic statements not present on the baseline assessments). The variety of morphology statements with the same meaning will be aggregated into defined categories by the Cardiac Safety Expert and incorporated into the analysis dataset. For example, T-wave inversion in Lead V2 and T wave flattening in Lead II will both be categorized as nonspecific T-wave abnormality.

Adequacy of HR Correction for ECG Report

The adequacy of the correction formula for QTcF will be assessed by determining the linear relationship of QTcF interval to RR. Adequacy will be defined as a population QTcF:RR slope of $< |0.045|$, and a slope of $< |0.045|$ in at least 50% of individual subjects. If QTcF interval is determined to be an inadequate correction, the QT interval with a study specific QTcSS will be calculated.

ECOG Performance Status

Individual subject ECOG performance status will be listed in Listing 16.4.4. The ECOG performance status will be summarized descriptively as Table 14.1.2.

Local Injection Site Reaction

Individual subject Local Injection Site Reaction will be listed in Listing 16.4.5. The local injection site reaction as recorded by Grade 0 (None), Grade 1 (Mild), Grade 2 (Moderate) and Grade 3 (Severe) will be summarized descriptively as count and percentage as Table 14.3.9.

Bone pain and urinary sign and symptoms (I-PSS)

Individual subject Bone pain and urinary sign and symptoms will be listed in Listing 16.4.6~ Listing 16.4.8. The summary results of VAS scale for bone pain measurement at baseline, EOS/ET Visit

Statistical Analysis Plan

and the change from baseline will be summarized descriptively in Table 14.3.10.1. Also, the change from baseline to EOS/ET visit will be tested by paired t-test or Wilcoxon signed-rank test at a significance level of 0.05. The urinary sign and symptoms at baseline and EOS/ET Visit will be summarized descriptively as Table 14.3.10.1. The transition status for urinary sign and symptoms by each scale* will be presented as Table 14.3.10.2. The quality of life will be presented as Table 14.3.10.3.

*For Urinary signs and symptoms Q1-Q6: 0 - None, 1 - Less than 1 time in 5, 2 - Less than half the time, 3 - About half the time, 4 - More than half the time, and 5 - Almost always.

For Urinary signs and symptoms Q7: 0 - None, 1 - 1 time, 2 - 2 times, 3 - 3 times, 4 - 4 times, 5 - 5 or more times.

For Urinary signs and symptoms quality of life: 0 - Delighted, 1 - Pleased, 2 - Mostly Satisfied, 3 - Mixed, 4 - Mostly Dissatisfied, 5 - Unhappy, 6 - Terrible

Unscheduled Assessments

The unscheduled assessment will be listed in Listing 16.4.9.

Telephone Contact

The telephone contact information will be listed in Listing 16.4.10.

12.COMPUTER METHODS

All statistical analyses will be conducted using SAS[®] software, Version 9.3 of the SAS System for Windows 7. Copyright[©] 2013 SAS Institute Inc. SAS and all other SAS Institute Inc. product or service names are registered trademarks or trademarks of SAS Institute Inc., Cary, NC, USA.
